We will establish the relationship between PUAL, estimated remifentanil concentration, and incidence and onset of OIRD indicated by decline in SpO2 < 90% in an extended age range (40-60 years). In this older age group, we will examine the magnitude and consistency of the opioid-PUAL relationship and compare risk of OIRD at various ranges of PUAL and estimated opioid effect site concentration. The purpose of doing so is to establish PUAL's validity in discriminating risk of OIRD across a broader population, and to determine whether the PUAL OIRD prediction scale requires modification or is invalid in older subjects. The overall goal is to extend the benefit of sensitive opioid monitoring across a broader patient population.

BACKGROUND AND RATIONALE

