In each 35-minute test sequence, vital signs will be continuously monitored with pupillary measurements taken every 2.5 minutes. During the first 10 minutes of the 35-minute sequence, remiferitanil will be infused at a predetermined rate described below. Sedation assessment will be made using the Pasero Opioid-Induced Sedation (POSS) Scale.²⁹

Opioid Infusion:

The remifentanil will be infused for 10 minutes- at a rate of 0.2µg/kg/minute for the first 5 minutes, followed by 0.3µg/kg/minute for the next 5 minutes. After remifentanil discontinuation, pupillary measurements will continue every 2.5 minutes for the remaining 25-minute recovery phase. To avoid the costs and stimulating effect of sequential blood drawing, or the added discomfort of arterial line placement to facilitate repeated blood sampling, we do not plan to measure remifentanil blood concentration, choosing instead to use an infusion protocol based on the Minto model that, when given to eligible subjects, should achieve an estimated maximum effect site concentration of 4-6 ng/mL, a level known to produce near-maximum isoflurane MAC reduction and high probability of apnea.²⁹⁻³¹

Outcomes:

Primary outcome is the correlation between PUAL and intensity of opioid exposure (represented by time-points corresponding to progressively increasing and declining estimated opioid concentrations) and the ability to discriminate zero-moderate versus high-toxic opioid effect. The discrimination of PUAL to identify high-risk opioid exposure will be determined by construction of receiver operator characteristic (ROC) curves.

Subjects:

Eligible subjects will be 40-60 years of age, recruited from flyers posted around the UCSF campus, and from an advertisement placed on Craigslist. Exclusion criteria will include use of opioid agonist or antagonist within the prior thirty days, any cardiopulmonary or neurologic condition, baseline SpO2 < 95%, diabetes, obstructive sleep apnea (OSA), BMI > 35 kg/m2, current or previous substance use disorder, ocular disease (including glaucoma), prior ocular surgery, use of any prescription ocular medication, use of medications known to affect pupillary characteristics (see below), blindness, previous episodes of serotonin syndrome, or inability to provide written informed consent.

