Use of any alpha-adrenergic blocking medication for urinary symptoms or anticholinergic medications

History or ocular surgery (ie, cataract surgery, vitrectomy), ocular disease (ie, glaucoma), or use of topical eye medications

Use of mood stabilizers or antidepressant medications (including serotonin-reuptake inhibitors or MAO-inhibitors) within past 30 days

Use of stimulant medications (amphetamines, including medications used for appetite suppression or attention deficit disorder)

Use of phosphodiesterase inhibitor medications (usually given for erectile dysfunction) within the past 7 days

Inability to read or understand English

Any condition prohibiting delivery of oxygen by nasal cannula

Anxiety or panic disorders

Severe motion sickness or intractable vomiting after prior anesthesia

Fever, upper respiratory infection, or illness of any variety within 8 weeks of participation

Exclusion criteria involving opioid use or substance use disorder will be determined by self-report from the potential subject.

DATA COLLECTION

Subject data including subject number, initials, age, sex, race, height and weight, along with time-stamped drug administration and vital signs, will be collected on a source document anesthetic record, which will be scanned and stored on a HIPAA-compliant secure location. Pupillary measures will be collected on a Neuroptics PLR-3000 device, and the date and times of the scans will be correlated to the times of each subject's data. The pupillary scans will be downloaded by Bluetooth to a csv file that will be stored on an encrypted laptop computer.

DATA ANALYSIS

We plan to test 20 subjects aged 40-60 under paired conditions- absent versus uninterrupted conversational interaction- over a 35-minute period. Interim analysis is planned after 10 subjects are studied.

Correlation between PUAL and opioid concentration:

We will examine PUAL and estimated opioid effect site concentration during both drug infusion (0-10 minutes, where opioid concentrations progressively increased) and recovery (10-35 minutes, where opioid concentrations progressively decline). Each 2.5-minute point will be treated as an ordinal variable "time", and opioid effect-site concentrations will be calculated at each time point according to the Minto pharmacokinetic model estimates.²⁹ The effect of time (as surrogate for opioid concentration) on PUAL will be assessed using a linear mixed effects model.

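### The plan calculates effect-site concentration at every reading but models PUAL only on ordinal time, so no change in PUAL per ng/mL is estimated.

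*Combined protocol and SAP*

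**What the plan says.** The Aims section states "We will establish the relationship between PUAL, estimated remifentanil concentration, and incidence and onset of OIRD", and goes on to ask how large and how consistent the relationship is in the older group.

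Under Outcomes, "Primary outcome is the correlation between PUAL and intensity of opioid exposure", together with the ability of PUAL to discriminate by ROC curve. The same sentence defines the exposure: "intensity of opioid exposure (represented by time-points corresponding to progressively increasing and declining estimated opioid concentrations".

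Under Data Analysis, in the part headed Correlation between PUAL and opioid concentration:

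- "We will examine PUAL and estimated opioid effect site concentration during both drug infusion" and recovery. No method is attached to this.
- "Each 2.5-minute point will be treated as an ordinal variable".
- "opioid effect-site concentrations will be calculated at each time point according to the Minto pharmacokinetic model estimates".
- The one model specified is a linear mixed effects model with time as predictor, standing in for concentration: "The effect of time (as surrogate for opioid concentration) on PUAL will be assessed using a linear mixed effects model".

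The next part of Data Analysis uses concentration to class readings as low (<2.0 ng/mL) or high (>2.4 ng/mL) for the ROC analysis and the interval likelihood ratios.

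**The concern.** The quantity of interest is computed and then not used as a predictor. This matters in two ways.

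First, time is not monotone in exposure. The same estimated concentration occurs once on the way up and once on the way down, so the effect of time changes sign at 10 minutes. If ordinal means a score with one trend across the session, the model mostly misses the exposure. If it means a factor, the model follows exposure but answers whether PUAL changes during the session, not by how much per ng/mL. The plan leaves this open and does not say whether the two phases are modelled separately.

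Second, a slope or curve on the concentration scale is the natural summary of the magnitude sought in the Aims, and the one that could be set beside another cohort or another infusion regimen. As written, the trial could finish with a significant time effect and a good ROC curve, but with no prespecified estimate of the concentration-response relationship.

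**Working it through.** **Plan's own figures.** There is no power or precision figure for the mixed model to reproduce. The sample size section rests on the AUROC and the likelihood ratios, so this point leaves it unchanged.

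**Inputs from the documents.** Readings every 2.5 minutes over 35 minutes give 35/2.5 + 1 = 15 time points: 5 in 0-10 minutes and 11 in 10-35, with the 10-minute reading shared. Infusion lasts 10 minutes and recovery 25. The regimen "should achieve an estimated maximum effect site concentration of 4-6 ng/mL". There are 20 subjects.

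**Assumed, because the documents give no concentration curve.** A linear rise to 5 ng/mL (the middle of 4-6) at 10 minutes, then C(t) = 5 × 0.5^((t-10)/h), with half-life h from 2 to 8 minutes. This is an illustration, not output of the Minto model.

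**Step 1: one concentration at two times.** With h = 5, C is 5 × 5/10 = 2.5 ng/mL at 5 minutes and 5 × 0.5^(5/5) = 2.5 ng/mL at 15 minutes. These are the third and seventh readings: the same exposure with different time scores.

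**Step 2: correlation of time with concentration over all 15 readings.** For h = 5, the sum of cross-products is -122.3, the sum of squares of time is 1750 and that of concentration is 32.83. So r = -122.3/√(1750 × 32.83) = -0.51.

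| h (min) | r, 0-35 min | r² | r, 0-10 min | r, 10-35 min |
|---|---|---|---|---|
| 2 | -0.55 | 0.31 | +1 | -0.72 |
| 3 | -0.56 | 0.31 | +1 | -0.82 |
| 5 | -0.51 | 0.26 | +1 | -0.91 |
| 7 | -0.43 | 0.18 | +1 | -0.95 |
| 8 | -0.38 | 0.15 | +1 | -0.96 |

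The +1 follows from the assumed straight rise. With a rise that flattens towards the peak (30%, 60%, 80% and 100% of peak at 2.5, 5, 7.5 and 10 minutes) and h of 3 to 8, the values are +0.99 in infusion, -0.82 to -0.96 in recovery and -0.43 to -0.58 overall. One time trend thus captures roughly 15-34% of a typical subject's variation in concentration.

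**Step 3: time as a factor.** With 20 subjects, peaks drawn uniformly from 4-6 ng/mL and h of 3 to 8, a 15-level time factor captures about 96-98% of the variation in concentration. Tracking is good, but the output is 14 contrasts between clock times and no coefficient per ng/mL.

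**Step 4: fit to PUAL.** In a simulation with the same peaks, exponential decline of PUAL with concentration and residual SD 0.03, the share of within-subject PUAL variance explained was about 28% for linear time, 70% for own concentration, 79% with a quadratic term added, and 81% for time as a factor. Concentration therefore does not fit better than a time factor; what it adds is interpretability. The gain from the quadratic term shows that a straight line in concentration should not be assumed.

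**The case against.** The strongest reply is that the surrogate is disclosed. The primary outcome itself represents exposure by time-points, so the time model is the analysis of that outcome and not a departure from it. With one fixed regimen for all subjects, time as a factor or split by phase is a close proxy. All of this stands. Disclosure does not supply a per-ng/mL estimate, however, and the coding that would make time a good proxy is not stated.

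Three stronger readings are tempting, and the documents do not support them.

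- A reader might infer that the relationship between PUAL and concentration is never estimated. That is too strong. The ROC analysis classes readings by estimated concentration, and the plan says that PUAL and concentration will be examined in both phases. What is missing is a specified analysis on a continuous scale.
- A reader might infer that the time model discards precision because subjects differ in peak concentration. The illustration does not bear this out. A rerun with half-life 3 or 5 minutes, baseline PUAL 0.2-0.3 and a decline rate of 0.5-1.2 per ng/mL gave 59-84% of within-subject variance explained by own concentration and 60-84% by one curve shared by all subjects. Also, 4-6 ng/mL is given as the intended range for the estimated maximum, not as a forecast of spread at each minute.
- A reader might infer that the time model undermines the comparison with the 20-39-year-olds. The planned formal comparison is of ROC curves, with readings classed by concentration, so it does not depend on the time model.

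It is also fair to say that individual concentrations here are predictions: the plan takes no blood samples. Modelling them cannot fully separate true exposure from sensitivity.

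**Conclusion.** The point holds in a limited form. The only model specified for the PUAL-concentration part of the primary outcome uses ordinal time, although concentration is calculated at each reading. If time enters as one trend over 0-35 minutes, the surrogate is poor (r about -0.4 to -0.6 across the assumed curves). If it enters as a factor or by phase, the surrogate is good but the magnitude named in the Aims is not obtained on a continuous scale.

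The size rests on assumed rise-and-fall curves; actual Minto predictions would change the correlations but not the rise and fall. That concentrations would be computed for each subject is an inference. It is supported by the ROC section, which refers to concentrations in all subjects, and by the collection of age, sex, height, weight and time-stamped dosing. No stated power, sample size or ROC result is affected. This is an inexpensive improvement and does not invalidate the plan.

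**What to change.** Under the correlation heading of Data Analysis, prespecify a mixed model of PUAL on each subject's calculated effect-site concentration at each reading, using the time-stamped dosing record. Include a subject random effect and an infusion/recovery phase term. Allow curvature in a form fixed in advance, for example a quadratic term or a log scale. If a log is used, state how zeros are handled, since baseline concentration is zero and the PUAL scale has zero as its lower bound.

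Keep the time model as supportive, with time coded as a factor.

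As a secondary analysis, where concentrations for the 20-39-year-olds are available, fit the same model to both cohorts with an age-group by concentration term. State which of the younger cohort's infusion sequences enter.

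The cost is a short paragraph and a little analysis time, with no new subjects or measurements. The downsides are small: the predictor is modelled and not measured, the functional form must be chosen beforehand, and random slopes may not be estimable with 20 subjects, so a random-intercept fallback should be named.

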Distinguishing between zero-low risk versus high-risk, toxic opioid conditions by PUAL: We will collect PUAL data at times when estimated opioid effect site concentrations in all subjects are consistently low (< 2.0 ng/mL) versus high (>2.4 ng/mL). A receiver operating characteristic analysis using dichotomized PUAL values will be constructed to determine PUAL's ability to distinguish between low-risk versus high-risk opioid exposure in the 40-60year-old subjects. This ROC curve will be compared to that of subjects in the 20-39 year-old range, and interval likelihood ratios that identify high, indeterminant and low risk will be reported.

SAMPLE SIZE CALCULATION

The primary objective of this study is to assess PUAL's ability to identify high-risk opioid effect in older adults. In the previous study in younger adults, we used a remifentanil infusion that consistently produced zero to moderate opioid effect at 2 time points (baseline and 2.5 minutes) and high opioid effect at 4 time points (5.0, 7.5, 10.0, and 12.5 minutes). We assessed the ability of PUAL to discriminate using the area under the ROC curve (AUROC).

In that study the AUROC was slightly *lower* under quiet vs. interactive conditions (0.95 vs 0.97), and the standard error of the summary AUROC was 0.01. If the discrimination is substantially lower in older adults, we would expect an AUROC of 0.875. A sample size of 20 participants would produce a 95% confidence interval of width 0.12 (0.81 to 0.93) and a standard error of 0.0275.³⁷ The standard error of the difference in AUROCs would be 0.03 and would provide 80% power to detect a difference in AUROCs of 7.5% at the 0.05 significance level.³⁸

In addition, we intend to evaluate the same PUAL intervals as found in our previous analysis of 20-39-year-old subjects:

- PUAL 0.00 to <0.04 = high-risk opioid effect, interval likelihood ratio = 14.59;
- PUAL \geq 0.04 to 0.13 = indeterminate effect, interval likelihood ratio = 1.12;
- PUAL \ge 0.14 = zero or low risk opioid effect, interval likelihood ratio = 0.02.

We will calculate interval likelihood ratios in the 40-60-year-olds.³⁹ For high opioid effect, we expect an interval likelihood ratio of approximately 10. Our sample size of 20 should allow estimation with a 95% confidence interval 3.3 to 30.

References:

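### The ROC sentence dichotomizes PUAL against the rest of the plan, no within-subject variance is given for the AUROC or likelihood ratios, and the stated SE does not give the stated interval

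*Combined protocol and SAP*

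**What the plan says.** **Analysis.** Under DATA ANALYSIS, the paragraph on distinguishing low-risk from high-risk conditions first splits exposure by estimated effect-site concentration (below 2.0 against above 2.4 ng/mL). It then says "A receiver operating characteristic analysis using dichotomized PUAL values will be constructed". The next sentence adds "This ROC curve will be compared to that of subjects in the 20-39 year-old range", and also that "interval likelihood ratios that identify high, indeterminant and low risk will be reported". The Outcomes section likewise plans ROC curves.

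**Readings per subject.** PUAL is measured every 2.5 minutes in each subject. The SAMPLE SIZE CALCULATION section reports that the earlier study had "zero to moderate opioid effect at 2 time points (baseline and 2.5 minutes) and high opioid effect at 4 time points". The current plan does not list its own qualifying time points. DATA ANALYSIS describes testing "under paired conditions- absent versus uninterrupted conversational interaction", whereas Design describes a single 35-minute regimen. PRELIMINARY DATA leaves open whether the younger comparator is the quiet arm or both sequences. A linear mixed effects model is named, but only for the effect of time on PUAL.

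**Precision.** For an expected AUROC of 0.875, 20 participants "would produce a 95% confidence interval of width 0.12 (0.81 to 0.93) and a standard error of 0.0275". The SE of the AUROC difference is given as 0.03. For a high-risk likelihood ratio of about 10, "Our sample size of 20 should allow estimation with a 95% confidence interval 3.3 to 30".

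**The concern.** The AUROC measures the stated primary objective, and the stated power is for the AUROC difference between age cohorts. Three things stand in the way of carrying this out as written.

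- **Wording.** A marker cut in two gives one sensitivity and specificity pair. That does not supply the curve, the like-for-like comparison with the younger cohort, or three-level likelihood ratios. A cut-point chosen later would be an unplanned decision made with the data in view.
- **Variance.** Readings from one person are likely to be correlated. If they are analysed as independent, the AUROC interval and the cohort test can be too optimistic, by an amount that depends on the correlation structure.
- **Arithmetic.** The SE and the interval that justify 20 participants appear in one sentence and do not agree.

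**Working it through.** **Inputs from the SAMPLE SIZE CALCULATION section.** AUROC A = 0.875; SE 0.0275; interval 0.81 to 0.93, width 0.12; SE of the younger cohort's AUROC 0.01; 20 subjects. If the earlier study's time points are reused, there are 4 × 20 = 80 high readings and 2 × 20 = 40 low readings.

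**1. The stated interval from the stated SE**
- Wald: 0.875 ± 1.96 × 0.0275 = 0.821 to 0.929, width 0.108.
- t with 19 df: 0.817 to 0.933, width 0.115.
- Logit scale: 0.810 to 0.920.

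None rounds to both 0.81 and 0.93. Working back, a width of 0.12 implies SE = 0.12/3.92 = 0.0306. The SE of the difference is √(0.0275² + 0.01²) = 0.0293, or √(0.0306² + 0.01²) = 0.0322. Both round to the stated 0.03, so that figure does not show which SE was meant.

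**2. Which number of readings fits**

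The Hanley–McNeil variance is [A(1−A) + (n₁−1)(Q₁−A²) + (n₀−1)(Q₂−A²)]/(n₁n₀), with Q₁ = A/(2−A) = 0.7778, Q₂ = 2A²/(1+A) = 0.8167 and A² = 0.7656.

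| High / low readings, taken as independent | SE | Wald width |
|---|---|---|
| 80 / 40 | √[(0.1094 + 0.9601 + 1.9906)/3200] = 0.0309 | 0.121 (0.814 to 0.936) |
| 20 / 20 | 0.0572 | 0.224 |
| 160 / 80 | 0.0218 | 0.085 |

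The planned width is far tighter than one independent reading per class per subject would give. It is close to 80 and 40 readings counted as independent. This is inference only.

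The likelihood-ratio interval does not settle it. With 60/80 high and 3/40 low, the SE of the log ratio is √(0.25/60 + 0.925/3) = 0.559, and 10 × exp(±1.96 × 0.559) = 3.34 to 29.9. Keeping 3/40 low, 30/40 high gives 3.32 to 30.1 and 120/160 high gives 3.36 to 29.8.

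**3. Effect of dichotomizing PUAL**

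As an illustration, assume equal-variance normal distributions with separation √2·Φ⁻¹(0.875) = 1.627. A true AUROC of 0.875 then becomes Φ(1.627/2) = 0.792 at the best single cut, so the result would not be comparable with an AUROC from a full curve.

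**4. Effect of ignoring repeated readings (simulation)**

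Assumptions: equal-variance normal readings, 20 subjects per cohort, intraclass correlation (ICC) within each exposure state, and a correlation between a subject's low-state and high-state effects. The interval that ignores clustering uses a DeLong-type SE. True AUROC is 0.875, with 10,000 runs per setting. Cells show true SE / independence SE, then coverage of the nominal 95% interval.

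| ICC, cross-state correlation | 4 high + 2 low | 8 high + 4 low |
|---|---|---|
| 0, 0 | 0.99, 93.0% | 1.00, 93.8% |
| 0.3, 0 | 1.18, 87.3% | 1.43, 81.5% |
| 0.3, 1 | 0.93, 93.9% | 0.98, 93.4% |
| 0.7, 0 | 1.43, 79.8% | 1.94, 66.9% |
| 0.7, 0.5 | 1.19, 86.4% | 1.61, 75.7% |
| 0.7, 1 | 1.00, 90.5% | 1.29, 83.3% |

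- **False differences** when both cohorts truly have AUROC 0.95 (nominal 5%): 3.7% to 14.5% with 4 + 2 readings in both cohorts. If only the younger cohort uses both sequences (8 + 4), 5.9% to 21.9%.
- **High-risk likelihood ratio:** the independence interval covers 92.5% to 95.6% at 4 + 2 and 88.6% to 94.6% at 8 + 4.
- **With subject-clustered variance:** the logit interval with t(19) covers 93.7% to 95.6%. The difference test rejects in 1.7% to 4.8% when the cohorts are equal. The log likelihood ratio with t(19) covers 96.3% to 97.3% of estimable runs. At 4 + 2, no low reading falls in the high-risk interval in 5% to 8% of runs.

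**The case against.** The intended analysis can be recovered from the surrounding text: PUAL is the score and exposure is the binary variable, so the first part is an editorial correction. The qualifying time points could be derived from the concentration rule and the named pharmacokinetic model before any PUAL value is seen. The 8 + 4 scenario for the older cohort rests on one phrase that conflicts with Design and may be left over from the earlier two-sequence study. All correlations are assumed. At 4 + 2 the SE ratio runs from 0.93 to 1.43, so even the direction of the error is not established, and a common ICC may not suit a measure with a floor at zero. The 80/40 reading count does not reproduce SE 0.0275; 100/50 would (0.0276). The interval mismatch is about 0.01.

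Much of this stands as a limit on size. The 67% figure should carry little weight for the older cohort, although both sequences are a real option for the younger one. The reading count behind the sizing remains unknown. None of it supplies the missing method. The two statistical references are attached only to the sizing figures, and the mixed model does not extend to the ROC or likelihood-ratio analyses. A probable slip in the only sentence that specifies the primary ROC analysis still needs correcting.

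**Conclusion.** The concern holds in all three parts, and the plan should be corrected.

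- The ROC sentence contradicts the analyses planned beside it. This rests on the text alone.
- No variance allowing for repeated readings is stated for the AUROC, the AUROC difference or the likelihood ratios. An independence analysis could be about right or too narrow. The low ends for the AUROC and its difference need an ICC of 0.7 with uncorrelated low-state and high-state effects; with fully shared effects at 4 + 2, coverage is 90% to 94%. The likelihood ratios are little affected at 4 + 2.
- SE 0.0275 and 0.81 to 0.93 do not agree. The discrepancy is small, and the documents do not show which figure is wrong.

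Confidence is high for the contradiction, the omission and the arithmetic. The size of the clustering effect is conditional on the assumed correlations.

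**What to change.** 1. Replace the ROC sentence with: *ROC analysis of continuous PUAL against dichotomized exposure (<2.0 vs >2.4 ng/mL), by the same method in both age cohorts.* Keep the pre-set PUAL intervals for the likelihood ratios only. List the qualifying time points, and state whether the younger data are the quiet arm or both sequences.
2. Specify a variance clustered on subject:
   - for the AUROC, on the logit scale with a t reference (subjects minus 1);
   - for the difference, the sum of the two cohorts' clustered variances with a t reference;
   - for the likelihood ratios, a clustered variance of the log ratio with a t reference and a stated rule for an empty cell.

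   Other subject-level methods are possible, but a plain percentile bootstrap by subject should not be relied on with 20 subjects: in a check at 4 + 2 it covered 89% to 92%.
3. Reconcile SE 0.0275 with 0.81 to 0.93. State the number of readings and the independence or correlation assumption behind the AUROC and likelihood-ratio intervals, and give a range under stated within-subject correlations.

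**Cost.** A few corrected sentences and a subject-level variance, with no change to design, conduct or data collection. Intervals may be somewhat wider, clustered methods are approximate with 20 subjects, and the clustered test of the difference is conservative in some settings (2% to 5% at nominal 5%).

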Opioid-induced respiratory depression (OIRD) confers significant safety risk, but its onset can be challenging to recognize. Hypoxia and related sequelae from OIRD may present abruptly, giving the clinician insufficient time to intervene and rescue before harm reaches the patient. Previous data showed that among healthy 20-39-year-old volunteers, incremental decline and eventual obliteration of pupillary unrest in ambient light (PUAL) occurred in a consistent manner during escalating opioid concentration from remifentanil infusion. Low and often obliterated PUAL were consistent markers of high-risk remifentanil exposure and coincident episodes of hypoxic respiratory depression, even while subjects remained alert. In this young adult age group, specific PUAL values discriminated between zero or low versus high-risk intensive opioid exposure with outstanding discrimination (AUROC = 0.9671 [0.9384 – 0.9958]).¹ We anticipate PUAL will develop into a useful tool in the future to guide clinical decision-making in patients receiving opioids on matters including choice of appropriate level of monitoring, consideration of supplemental oxygen, possible opioid de-escalation, and timely pursuit of non-opioid analgesic alternatives and support when necessary. To explore the generalizability of these findings, we plan to perform a similar study among subjects in an older age range (40-60 years). Although we anticipate that the PUAL decline and opioid intensity relationship will probably be similar across age ranges, the predictive value of specific PUAL thresholds may differ in older individuals due to age-related changes in normal pupil measurements and characteristics. Recent unpublished data from ambulatory subjects showed a modest decline in resting PUAL in subjects aged 50 and older compared to younger adult subjects. The physiologic vulnerability of older patients elevates the importance of early, reliable OIRD detection. Aging is accompanied by alteration of a variety of vital protective mechanisms, including blunting of chemoreceptormediated ventilatory responses to hypoxia and hypercapnia.^{2,3} Among subjects with sleep disordered breathing, older age is associated with more severe, prolonged desaturation episodes during upper airway obstruction.³

AIMS

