Subsequently we studied 20 healthy volunteers aged 20-39 years, to determine whether progressive decline of PUAL to zero or a lower limiting value would occur consistently as opioid exposure increased to the point of respiratory depression.¹ Participants received an intravenous infusion of remifentanil, an ultra-short acting opioid medication. As the dose and effect site concentrations incrementally rose, serial pupillary measures were taken every 2.5 minutes, including at times coinciding which clinically significant respiratory depression. We sought to determine whether PUAL declines consistently to zero or near zero in all subjects as opioid concentration builds to the point of respiratory depression. We found that in this group of participants aged 20-39, PUAL declined significantly over the course of the remifentanil infusion and rose significantly during recovery (p < 0.0001). Nearly all subjects reached 90% or greater PUAL suppression. PUAL showed outstanding discrimination in

distinguishing higher versus absent-moderate opioid exposure (AUROC = 0.957 [0.929 to 0.985] in all runs). For exploratory purposes this study had two infusion sequences, one conducted under normal "quiet" conditions, and the other during stimulating "interactive" conditions to estimate what if any role environmental stimulation may play in delaying or mitigating OIRD. Findings in younger subjects used for subsequent comparison to the older group will use the data from the control ("quiet") arm, or from both infusion sequences as appropriate.

In a separate study, to estimate normative ranges of PUAL in the general population across age groups, we evaluated 150 de-identified ambulatory subjects, collecting information only on age-range, (18-29, 30-49, 50-69, and \geq 70 years), diabetes, and use of opioid or beta-blocker medication in the previous 24-hour period. In that cohort we found a modest but statistically significant impact of age on PUAL, where subjects \geq 50 years of age had lower median PUAL values versus subjects under 50 years of age.

EXPERIMENTAL DESIGN AND METHODOLOGY OF PROPOSED STUDY

Design:

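### The primary ROC analysis is specified on dichotomized PUAL with no cut-point, and so does not match the AUROC used for the younger benchmarks and the sample size

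*Combined protocol and SAP*

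**What the plan says.** The Outcomes paragraph makes discrimination part of the primary outcome: "The discrimination of PUAL to identify high-risk opioid exposure will be determined by construction of receiver operator characteristic (ROC) curves".

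The Data Analysis section, in its paragraph on separating low-risk from high-risk exposure, first splits estimated effect-site concentration into low (<2.0 ng/mL) and high (>2.4 ng/mL). It then says "A receiver operating characteristic analysis using dichotomized PUAL values will be constructed", gives no cut-point, and continues: "This ROC curve will be compared to that of subjects in the 20-39 year-old range".

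The Sample Size Calculation works with AUROCs. It reports the younger cohort as "under quiet vs. interactive conditions (0.95 vs 0.97), and the standard error of the summary AUROC was 0.01" and then states: "If the discrimination is substantially lower in older adults, we would expect an AUROC of 0.875". Preliminary Data gives the younger result as "AUROC = 0.957 [0.929 to 0.985] in all runs", and the opening background section gives 0.9671. None of these figures is described as coming from a single cut.

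**The concern.** PUAL is a continuous measure. An ROC curve sweeps a threshold across it while the reference state, here low or high exposure, is binary. As written, the sentence makes the test binary too. A two-level test has one operating point, so the curve is two straight segments with area (sensitivity + specificity)/2. For any concave curve that is not already a single step, that area is below the full-curve AUROC.

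Two things are at stake. First, an analyst who follows the sentence must choose a cut. The plan does not say whether to fix it from the younger cohort or to choose it in these 20 subjects, and the latter would add optimism. Second, the result is to be set beside the younger curve, and the Aims say the study will inform whether the PUAL scale needs modification or is invalid at older ages. A fall in area caused by the analysis scale would bear directly on that judgement.

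**Working it through.** **1. The plan's own figure.** Inputs from the Sample Size Calculation: AUROC 0.95 versus 0.875 (difference 0.075), SE of the older AUROC 0.0275, SE of the younger AUROC 0.01.

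- SE of the difference = √(0.0275² + 0.01²) = 0.0293, stated as 0.03.
- Power = Φ(0.075/0.03 − 1.645) = Φ(0.855) = 80.4% one-sided. This matches the stated 80%. Two-sided, Φ(2.5 − 1.96) = 70.5%.

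The calculation therefore concerns full-curve AUROCs with AUROC standard errors.

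**2. Area left after a single cut.** Assume an equal-variance binormal curve, which the documents do not give. The best cut gives area Φ(z(AUROC)/√2).

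| Full-curve AUROC | Source | Best single-cut area |
|---|---|---|
| 0.95 | Sample Size, quiet | Φ(1.645/1.414) = 0.878 |
| 0.957 | Preliminary Data, all runs | 0.888 |
| 0.9671 | Opening background | 0.903 |
| 0.875 | Sample Size, older | 0.792 |

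**3. Range around 0.878, starting from 0.95.**

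- Cuts at other points, with specificity from 0.70 to 0.95: sensitivity = Φ(√2 × 1.645 − z(specificity)). At specificity 0.70 this is Φ(2.326 − 0.524) = 0.964, so the area is (0.964 + 0.70)/2 = 0.832. Overall the areas run from 0.83 to 0.88.
- Unequal variances, best cut: 0.898 at an SD ratio of 2 and 0.931 at a ratio of 4.

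The illustrative range is therefore about 0.83 to 0.93.

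**4. A check without normality.** Take the plan's interval likelihood ratios (14.59, 1.12, 0.02) and any concave curve with AUROC 0.95. Let q be the share of low-exposure readings in an interval. The smallest middle share compatible with 0.95 is 0.118. The shares in each exposure group must sum to 1, so:

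- q for PUAL <0.04 = (1 − 1.12 × 0.118 − 0.02 × 0.882)/(14.59 − 0.02) = 0.0584
- sensitivity at that cut = 14.59 × 0.0584 = 0.851
- area = (0.851 + 1 − 0.058)/2 = 0.897

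The same step at 0.14 gives 0.904. These are upper limits. With AUROC 0.957 or 0.9671 they rise to about 0.95 to 0.96, so the plan's likelihood ratios do not pin down the size of the loss.

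**5. Older cohort cut, younger curve left whole, no true age effect.** With SE 0.03, the two-sided probability of declaring a difference is Φ(gap/0.03 − 1.96) plus a negligible or small opposite tail.

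| Older area shown | Gap from 0.95 | False difference |
|---|---|---|
| 0.93 | 0.02 | 10% |
| 0.878 | 0.0724 | 67% |
| 0.83 | 0.12 | 98% |

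One-sided, 0.878 gives 78%. Replacing 0.03 by an SE suited to a single-cut older area (SE of the difference 0.033) gives 59% two-sided and 70% one-sided.

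**6. Both cohorts cut alike.** The expected difference under no age effect is 0. For power, take the design values under the model in step 2: 0.878 − 0.792 = 0.086. With 80 high and 40 low readings per cohort (20 subjects, 4 and 2 time points), SE = ½√(A(1−A)/80 + A(1−A)/40). This is 0.0317 at 0.878 and 0.0393 at 0.792. The SE of the difference is √(0.0317² + 0.0393²) = 0.0505, and one-sided power is Φ(0.0856/0.0505 − 1.645) = 52%, against the stated 80%. This treats repeated readings within a subject as independent.

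**The case against.** The strongest reply is that the word is misplaced. The sentence before it dichotomizes exposure, and the rest of the plan speaks of ROC curves and AUROCs, so a full curve was probably intended. That is plausible, but it supports correcting the text: as it stands, the word attaches to PUAL.

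A reader might infer that older adults with unchanged discrimination would score about 0.88 and be mistaken for the plan's 0.875 case. The documents do not support that as a prediction. It requires the older data to be cut while the younger curve is left whole, and the plan does not say so. Preliminary Data says the younger data, from the quiet arm or from both sequences, will be used for comparison, so the same method can be run on both. The value also depends on an assumed curve shape, the best cut and 0.95 as reference. Its closeness to 0.875 follows from those choices.

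A reader might also see a contradiction with the three-level interval likelihood ratios. The Sample Size Calculation introduces those as an additional evaluation, and they can stand beside an ROC analysis on any scale.

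Finally, the readings are stored, so nothing is lost at data collection. That is true, and it keeps the remedy cheap. It does not settle which analysis is pre-specified.

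**Conclusion.** Wrong as written. The stated rule for a primary analysis yields a single operating point at an unnamed cut, and it does not match the AUROC quantities used for the younger benchmarks and the sample size. This holds without any distributional assumption.

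The size of the consequence is conditional. If only the older cohort is dichotomized, an unchanged 0.95 could appear as about 0.83 to 0.93, with a false-difference rate of roughly 10% to 98% at the plan's SE. The values 0.878 and 67% are one point in that range. If both cohorts are dichotomized alike, no spurious age effect is expected. Discrimination information is still lost, the cut remains undefined and the 80% power no longer describes the test. The documents do not show that a false age effect will occur.

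**What to change.** Replace the sentence with: *ROC analysis of continuous PUAL against dichotomized effect-site concentration (low <2.0, high >2.4 ng/mL).* State that the same method will be applied to both cohorts' data. Confine PUAL categories to the interval likelihood ratios, at the cut-points already fixed from the younger cohort (0.04 and 0.14).

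If a two-level PUAL is truly intended, name the cut in advance, apply it to both cohorts, and redo the precision and power statements for that quantity.

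The recommended change costs one sentence of protocol wording, with no new data or subjects, and should be made before the data are analysed.
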